Harp's pharmacists will screen patients in their MTM program and enroll them in familial or peer clusters consisting of 1 or more subjects and randomize them into 1 of the 4 study arms using a site specific randomization schedule. Each arm will receive pre and post testing and health literacy evaluation. Two education arms will use the 139 page CKD: What You Need to Know workbook including the CKD Action Plan as self-study tools and follow-up during regular MTM appointment. The 3 arms include 2 education arms and a control arm with various levels of intervention: Arm 1) case management model including pharmacist initiated discussion of workbook content and action plan reinforcement, Arm 2) brief introduction of the workbook and action plan reinforcement, Arm and Arm 3) the control group will receive a list of web-based CKD sites and a copy of the action plan with no additional intervention. Patient initiated CKD discussions will be tracked by both the pharmacist and staff by topic and time spent. Time spent by the pharmacist and staff will be calculated along with outcomes and compared in each group. Data collected upon enrollment will include year of birth, race, gender, county of residence, history of CKD, diabetes, hypertension and/or heart failure, patient reported blood pressure, AIC, eGFR and hemoglobin, smoking history, renal transplant history and if is under the care of or has been seen by a nephrologist in the past.

The CKD: What You Need to Know Workbook is 139 pages and includes:

- An Introduction
- 8 Chapters plus resources:
 1. Kidneys and Chronic Kidney Disease (CKD)
 2. Protecting Your kidneys and Slowing CKD Progression
 3. Your Choices for Dialysis and Transplantation
 4. Lab Results: What they mean & What you can control
 5. Chronic Kidney Disease & Eating Habits

6. Chronic Kidney Disease & Meds
7. Learning to Cope with Kidney Disease
8. Paying for Your CKD Treatment
9. CKD Action Plan
10. Web-based Resources
11. Kidney Talk: What do these words mean?
12. Resources

Each section ends with “Frequently Asked Questions”, “Test Your Knowledge” and has space for notes. Patient testimonies are found at the back of 6 chapters.

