The workbook went through health literacy editing with a goal of a 5th grade reading level. The chapters ranged from 3rd to 7th grade levels. It was felt that it was important for subjects to learn or at least be exposed to words that were kidney related and frequently used by their health care providers. So the first time each of these words were used in the workbook they were red and the definition was in the kidney talk section on that page. Then the first time the word appeared in subsequent chapters the word was in red but no definition was on that page.

Subjects will be randomized into 1 of 2 education arms that offer various levels of support or a control arm using a site specific computer generated randomization schedule. Presumed monthly visits.

Study Arm	Handouts	Visit 1*	Visit 2	Visit 3	End of Study June 2022
Testing		Pre-test		Post-Test	Evaluation
1: Case Study Model	Workbook Action Plan (V1) Label reading Exercise (V2)	Pharmacist initiated review of workbook and assist with Action Plan goal selection	Action Plan Reinforcement. Discuss Chapters 1-4. Provide “Label Reading Exercise”	Action Plan Reinforcement. Discuss Chapters 5-8 and resources. Review results of Label exercise	Open conversations from each party for all arms after evaluation
2: Minimal Instruction	Workbook Action Plan	Briefly explain handouts with focus on Action Plan.(5-10 minutes)	Action Plan Reinforcement. Answer patient’s questions.	Action Plan Reinforcement. Answer patient’s questions.	As Above
3: Control	Resource List Action Plan	Answer patient’s questions.	Answer patient’s questions.	Answer patient’s questions.	As Above

*On first visit, education arms subjects will be asked to read 1 chapter of the workbook weekly. All subjects will receive a CKD Action Plan and be asked to set individual goals.

Secondary outcome data collected at each visit include both self-reported and/or

Title: Pragmatic Approach to Chronic Kidney Disease Education in the Delta V.6

PI: [name]

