pharmacist or physician confirmed blood pressure and AIC, eGFR, hemoglobin. Patient and/or pharmacist initiated CKD conversation and topics including CKD action plan goal progress. The action plan has 1 knowledge goal related to CKD cause, eGFR and trend and 10 performance goals based on international guidelines and best practices including AIC goal of 7 or less, blood pressure goal of less than 140/90, exercise goal of 30 minutes 5 times a week, medications that may need to be avoided (ex: ibuprofen) or may need to be taken (ex: Statin) if you have CKD and DM or over 50 years old), smoking cessation, kidney friendly diet (may need to modify salt, phosphorus and/or protein intake and be edema free [may require monitoring and adjust salt and water intake], home monitoring of blood pressure, blood sugar and weight, weight management and anemia (goal hemoglobin above 10g/dL)

Study Population

High Risk Subjects will be identified from the Harps MTM program or others having multiple known medical problems (CKD, HTN, DM or heart disease). Know Your Kidney Number Posters which will be available statewide by the time the study starts will be posted in the pharmacy. Even though they are not study specific, they provide pertinent CKD information that could motivate subjects to want to learn more about how to protect their kidneys. Study Patient information Sheets will be available for interested parties.

A total of 100 clusters of 1 or more people from familial or peers groups will be enrolled. The actual number of subjects will depend on the volume of clusters with more than 1 person. This would include approximately 1/3 of the Harps MTM subjects that have both DM and HTN.

Inclusion Criteria

- Adults (any gender)>18 years old
- Enrolled in Harp's MTM program
- Has Known CKD or 2 of the 3 conditions covered in MTM (DM, HTN and Heart Failure)
- Not on dialysis

Exclusion Criteria

- unable to read or speak English
- history of significant cognitive dysfunction unless qualified caregiver is the one being educated
- not personally independent or without any social support

Risks and Benefits

A risk to study participants is the potential for loss of confidentiality of study data.

Measures to protect the confidentiality of study data will be implemented as described in the Data Handling and Recordkeeping section below.

Title: Pragmatic Approach to Chronic Kidney Disease Education in the Delta V.6

PI: [name]

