Potential benefits include the education received can motivate changes that can protect their kidney function, slow CKD progression and empower them to become more active in their health care.

Ongoing monitoring of international guidelines will be done to ensure education goals remain current.

Data Handling and Recordkeeping

All data received from Harps will be de-identified prior to being sent to UAMS. UAMS study tools will be de-identified. At randomization, the subject will receive a study number including: Harps site #, enrollment #, study arm #, subject initials, and # of people in cluster. In clusters with more than 1 person, the leader will be 1, the 2nd person will be 2, the 3rd 3. The cluster members initials will not be used, they will link to the leader.

Example the first cluster in the study consists of 2 people at site 3 lead by John Doe and randomized to study arm 2. The study number would be 3.1.2.JD.1 for the leader and 3.1.2.JD.2 for the 2nd person.

Data sent to UAMS Research Team. Data can be submitted in REDCap or on Paper.

After Visit 1	Intake Sheet including that includes demographics and medical history, Pre-Test, List of Meds	
After Final Visit	Data Collection Sheet 1, Post-test, Program Evaluation & List of Meds	

EOS: death, start of dialysis or transplantation.

Data will be stored in the UAMS Research office with access limited to study personnel only. UAMS-maintained computers and servers will be used to maintain databased information.

The Principal Investigator will carefully monitor study procedures to protect the safety of research subjects, the quality of the data and the integrity of the study.

At the conclusion of the study, the data will be maintained and later destroyed in accordance with UAMS policy which is for seven years after final reporting or publication of a project, or longer if required by a sponsor or regulation. Any data from subjects who opt out will not be kept for future use.

Multisite Research

Harps district director and research coordinator will be responsible for the education and oversite of each of their sites and not be responsible to UAMS IRB oversight. UAMS will supply the educational tools for both pharmacist, their staff and study subjects. This will include the CKD: What You Need to

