Secondary outcomes will be compared in all clusters. Because randomization seldom results in samples that are balanced on all baseline characteristics, information on control variables relevant to choice of dialysis mode will be collected, including age, gender, baseline intent to start home based dialysis, whether currently being followed by a nephrologist, patient engagement measured by the percent of visits where CKD patient initiated discussion took place and self-reported and provider confirmed outcomes listed in study plan. Pharmacists and staff time will be compared between arms and linked to costs to support each intervention arm. Tests appropriate for the measure will be used when comparing baseline characteristics between the research arms.

The sample size was based on what was appropriate for what could be reasonably be accomplished in the time frame with the available funding. Power based on the primary aim was a secondary consideration. A population of 100 clusters could result in a much larger population of subjects depending on the size of the clusters. Utilizing clusters to essentially train peer educators and describe their training methods, as well as, the outcomes of each of their cluster members can inform future research involving CKD peer educator led CKD patient education programs.

Ethical Considerations

This study will be conducted in accordance with all applicable government regulations and University of Arkansas for Medical Sciences research policies and procedures. This protocol and any amendments will be submitted and approved by the UAMS Institutional Review Board (IRB) to conduct the study.

This study meets the criteria for exempt review and does not require formal consent of the subjects. However, a Patient Information Sheet explaining the study will be provided to interested parties. After discussion with Harp's pharmacist, verbal consent will be obtained and completion of the pre-test will be evidence of consent. UAMS will receive no HIPAA data on subjects. All data will be de-identified as outlined above and a HIPPA waiver has been requested.

Dissemination of Data

Results of this study may be used for presentations, posters, or publications. The publications will not contain any identifiable information that could be linked to a participant.

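### Follow-up A1C, eGFR and hemoglobin may be results drawn before randomisation, because the plan schedules no draw and requires no sample date or source

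*Combined protocol and SAP*

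**What the plan says.** Study Design and Procedures describes the data in two places. The enrollment data include "patient reported blood pressure, AIC, eGFR and hemoglobin". After the visit table, a sentence that runs over a page break begins "Secondary outcome data collected at each visit include both self-reported and/or" and continues "pharmacist or physician confirmed blood pressure and AIC, eGFR, hemoglobin" (AIC is A1C).

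The visit table is introduced by "Presumed monthly visits" and has three visits in every arm, with the pre-test at Visit 1, the post-test at Visit 3 and an evaluation at end of study in June 2022. Its footnote adds: "On first visit, education arms subjects will be asked to read 1 chapter of the workbook weekly". The workbook has 8 numbered content chapters.

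The submission list in Data Handling and Recordkeeping asks for an intake sheet, pre-test and medication list after Visit 1, and after the final visit for "Data Collection Sheet 1, Post-test, Program Evaluation & List of Meds". That section also says that data are de-identified before they reach the university team.

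On use, Data Analysis says "Secondary outcomes will be compared in all clusters". It also names "self-reported and provider confirmed outcomes listed in study plan" among the control variables.

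Neither the visit table nor the submission list contains a blood draw, a lab order, a sample date or a look-back window. No rule covers repeated values, mixed sources or missing results.

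**The concern.** Blood pressure can be measured at a pharmacy visit. A1C, eGFR and hemoglobin come from a blood sample, and this plan does not arrange one. What the site can enter at Visit 2 or Visit 3 is the latest result that the patient knows or a clinician can confirm. If no sample has been taken since Visit 1, that is the result already held at baseline.

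Such a value was fixed before the education began. Counted as follow-up, it contributes no expected difference between arms and dilutes whatever effect there is. A null lab comparison could then mean either that the education did not move these values or that many of them were never measured again. The analysts could not tell which from anything the plan requires, because they receive de-identified data with no required sample date.

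There is a second, weaker strand. Several sources are allowed and nothing keeps the source constant within a subject, so a recalled value at one visit may be set against a confirmed value at another.

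At stake are the secondary lab comparisons and the action plan goals tied to A1C and hemoglobin. The primary outcome, choice of dialysis modality, is not a lab value and is untouched.

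**Working it through.** The plan gives no testing frequency, effect size or standard deviation for the lab values, so it has no figure to reproduce. The check covers the length of the window and then the share of stale values under stated assumptions.

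**1. Window from Visit 1 to Visit 3.** Three monthly visits leave two gaps.
- 4-week months: 2 × 28 = 56 days = 8.0 weeks.
- Calendar months: 2 × 30.4 = 60.8 days = 8.7 weeks.
- Cross-check: 8 chapters at one a week = 8 weeks.

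**2. Is a new sample guaranteed in that window?** The enrollment data, visit table, secondary outcome sentence and submission list, read together, schedule no draw and require no date. Entering the same result at all three visits complies with each of them.

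**3. Share of stale values (assumed testing pattern).** Suppose routine tests fall every T days, with the starting point at random relative to Visit 1. For a window of w days, with w no longer than T:
- share with a new result: f = w / T
- share stale: 1 − f

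| Testing interval T | w = 56: new / stale | w = 60.8: new / stale |
|---|---|---|
| 91 days (quarterly) | 56/91 = 0.62 / 0.38 | 60.8/91 = 0.67 / 0.33 |
| 182 days (six-monthly) | 56/182 = 0.31 / 0.69 | 60.8/182 = 0.33 / 0.67 |
| 365 days (yearly) | 56/365 = 0.15 / 0.85 | 60.8/365 = 0.17 / 0.83 |

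For Visit 2 the window is one gap, 28 to 30.4 days. The stale share is then 67–69% (for example 1 − 28/91 = 0.69), 83–85% and 92% for the same three intervals.

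**4. Direction of the effect.** Let δ be the true difference between arms in a newly drawn value. A stale value has expected difference 0, because it precedes the education and arms are randomised. If f is the same in all arms, the expected observed difference is f × δ + (1 − f) × 0 = f × δ. This applies to Visit 3 levels as well as to change from baseline, since a stale Visit 3 level is a baseline level. The formula credits every new result with the full effect, even one drawn the day after Visit 1.

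**5. Source.** Enrollment values are described as patient reported. Visit values may be self-reported, confirmed, or both. The rule for each visit includes Visit 1, so the two descriptions may apply to the same contact. The text permits a change of source but does not establish one.

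**The case against.** The strongest case on the other side has five parts.

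- **Labs are marginal to the plan.** They are not named in Specific Aims, no change score is defined, the study is a pilot sized by feasibility, and the primary outcome is unaffected. This limits the importance of the point but does not remove it. The plan calls these values secondary outcome data and says that secondary outcomes will be compared.
- **The forms have not been seen.** The intake sheet and Data Collection Sheet 1 are named but not reproduced, and may already capture date and source. This stands, so the fix is conditional on it. Even with a date on the form, the text has no rule on which values count.
- **The 8 weeks is uncertain.** Monthly spacing is only presumed. Data Collection Sheet 1 travels with the program evaluation, which the visit table places in June 2022, so the last lab value may come later than Visit 3. This stands. A longer window would lower the stale share, by an amount nobody could determine without dates.
- **The percentages are not specific to this trial.** This also stands. The testing intervals are assumptions. The action plan's knowledge goal covers eGFR and its trend, so the education could itself prompt testing, and the share of new values could then differ by arm.
- **No bias between arms is shown.** A reader might infer that confirmed values would be commoner in Arm 1, where the pharmacist leads the discussion, or that baseline is recalled and follow-up confirmed. The documents support neither. One data-collection rule covers all subjects, every arm has three visits, and confirmation is nowhere linked to arm.

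**Conclusion.** The point holds for A1C, eGFR and hemoglobin as secondary outcomes. A site that follows the plan exactly can enter a result drawn before randomisation as follow-up, and nothing that the plan requires would reveal it. Such values cannot reflect the education and pull arm differences towards null.

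The size is unknown. The 33–38%, 67–69% and 83–85% shares at Visit 3 show what quarterly, six-monthly or yearly testing would imply. They rest on fixed testing intervals, random phase, testing unrelated to arm, and monthly visits. They are not estimates for this trial.

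A reader might go further and conclude that the lab comparison does not measure the intervention at all. The documents do not support that. Some values may be new, the forms may record dates, and the last value may postdate Visit 3. A change of source remains a possibility only.

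**What to change.** **Forms.** For each A1C, eGFR and hemoglobin on the intake sheet and Data Collection Sheet 1, unless the forms already do so, record:
- when the sample was drawn relative to Visit 1, as days from Visit 1 or as drawn after Visit 1 yes/no, which avoids calendar dates and fits the de-identification plan;
- the source: patient report, pharmacist, or physician record.

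**Analysis.** Add to Data Analysis that a value drawn before Visit 1 is not treated as a follow-up outcome, that the share of new values and of each source is reported by arm, and that lab comparisons are descriptive.

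**Cost.** No extra tests. Two entries for each of three measures on two forms is 2 × 3 × 2 = 12 entries per subject, or 2 × 3 × 3 = 18 if Visits 2 and 3 are recorded separately. Fewer follow-up values will be analysable. The subset with a new value is defined after randomisation and may differ by arm if the education prompts testing. That is why the comparison should stay descriptive and the shares be shown by arm.

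Two stricter rules may look attractive but are not recommended. Using only pairs from the same source adds further selection after randomisation. Requiring the last value up to June 2022 makes follow-up length depend on enrollment date.

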The tools being used were developed by a multidisciplinary team of nephrology experts which are limited in the delta. Courses including train the trainer classes for pharmacies and 10 points of Care for CKD for clinicians will be conducted. Collaboration with local providers can both educate and promote community engagement.

Harp pharmacists expressed randomization concerns. They report that many of their MTM subjects have multiple family members or friends enrolled in the study. This could confound randomization into various arms since these subjects are highly likely to compare and contrast the details of their intervention. It was decided that a cluster randomization schedule would be utilized with each cluster self-selecting a leader that would be enrolled in the study and be responsible for education of the other cluster

members. All cluster members will undergo the same testing.

Specific Aims

The primary aim is to assess the effectiveness of pharmacists and their staff to educate CKD and high risk patients evaluating effectiveness through patient choice of RRT in each arm (e.g. home dialysis choice rate). Secondary aims include 1) Identify actions patients are willing to take to protect their kidney function using the CKD Action Plan that contains 10 performance goals based on international CKD guidelines that can slow CKD progression 2). Describe outcomes and methods used by peer leaders to educate cluster members using the same goals. 4) Compare costs (based on pharmacist and pharmacy associate time) with outcomes in each arm.

Study Design and Procedures

This study is a randomized control pilot study using non-nephrology clinicians to educate patients who are at high risk for CKD how to protect their kidneys and be ready for RRT if and when needed by utilizing nephrology developed educational tools.

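### Action Plan goal progress is described only as a conversation topic, and those conversations are scheduled in the education arms but not in control, so recorded progress can differ by arm without any true difference

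*Combined protocol and SAP*

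**What the plan says.** Secondary aim 1 in Specific Aims is to "Identify actions patients are willing to take to protect their kidney function using the CKD Action Plan that contains 10 performance goals". Aims 2 and 4 draw on the same material: outcomes of peer-led cluster members judged on the same goals, and staff cost set against outcomes in each arm.

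Study Design and Procedures opens its list of secondary data with "Secondary outcome data collected at each visit include both self-reported and/or" and then names blood pressure, A1C, eGFR and hemoglobin. Goal progress enters in the next item: "Patient and/or pharmacist initiated CKD conversation and topics including CKD action plan goal progress". Neither item is limited to an arm.

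The visit table differs by arm. Arms 1 and 2 both have Action Plan Reinforcement at Visits 2 and 3. At every visit the control row lists only the answering of questions, and the narrative says that "the control group will receive a list of web-based CKD sites and a copy of the action plan with no additional intervention". A footnote to the table applies to everyone: "All subjects will receive a CKD Action Plan and be asked to set individual goals".

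Data Handling and Recordkeeping lists one set of forms for all subjects. After Visit 1 these are an intake sheet, the pre-test and a medication list. After the final visit they are Data Collection Sheet 1, the post-test, the program evaluation and a medication list. The content of Data Collection Sheet 1 is not described. Data Analysis says that secondary outcomes are compared in all clusters and makes no provision for differences in how they were elicited.

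**The concern.** Read as written, the contact that delivers the intervention is also the contact that reveals the outcome. A pharmacist reinforcing the plan in Arm 1 or 2 will naturally learn what the subject has done about each goal. In control, before the open conversations at the end of the study, progress comes up only if the subject mentions it. A control subject who has started exercising and says nothing may be recorded like one who has not.

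A difference in recorded progress between arms would then mix a true effect with a difference in ascertainment, and the data could not separate them. The cost comparison has the same weakness. If more staff time means more conversation, and more conversation means more recorded progress, time and outcome are linked partly by the method of recording.

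**Working it through.** The plan states no figure for this outcome, so there is nothing to reproduce. The check sets the relevant text side by side and then illustrates the mechanism.

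**Step 1: who is asked, and when**

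| Item | Arm 1 | Arm 2 | Control |
|---|---|---|---|
| Asked to set goals (table footnote) | Yes | Yes | Yes |
| Visit 1 support (visit table) | Pharmacist review and help choosing goals | Short explanation centred on the Action Plan | Questions answered |
| Visits 2 and 3 (visit table) | Reinforcement plus chapter discussion | Reinforcement plus questions answered | Questions answered |
| Scheduled contact that would bring out progress before end of study | Yes | Yes | None listed |
| Standard form stated to record progress | None stated | None stated | None stated |

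The arms match on the request to set goals. They differ on scheduled contact about progress.

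**Step 2: which goals are exposed**

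Blood pressure, A1C and hemoglobin are both Action Plan goals and data items collected at each visit with no arm restriction. The medication goal can be informed by the two medication lists. Exercise, diet and home monitoring have no such separate source in the documents. The point applies to goals of this second kind.

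**Step 3: illustration under assumed rates**

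Let p be the true progress rate, the same in both arms. Let a_E and a_C be the probabilities that progress is recorded in an education arm and in control. Unrecorded progress is counted as none. Then:

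- recorded rates: p × a_E and p × a_C
- spurious difference: p × (a_E − a_C)
- apparent odds ratio: [p·a_E / (1 − p·a_E)] / [p·a_C / (1 − p·a_C)]

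For p = 0.50, a_E = 0.90 and a_C = 0.50, the recorded rates are 0.45 and 0.25. The difference is 20 points and the odds ratio is (0.45/0.55)/(0.25/0.75) = 2.45.

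The last column below is the chance of a significant result favouring education (two-sided 5% test of two proportions). It assumes 33 single-person clusters per arm, which is 100/3 with equal allocation to three arms. The plan does not state the ratio.

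| p | a_E | a_C | Recorded | Odds ratio | False significant result |
|---|---|---|---|---|---|
| 0.30 | 0.90 | 0.70 | 27% v 21% | 1.39 | 8% |
| 0.30 | 0.90 | 0.50 | 27% v 15% | 2.10 | 22% |
| 0.30 | 0.90 | 0.30 | 27% v 9% | 3.74 | 48% |
| 0.50 | 0.90 | 0.70 | 45% v 35% | 1.52 | 13% |
| 0.50 | 0.90 | 0.50 | 45% v 25% | 2.45 | 40% |
| 0.50 | 0.90 | 0.30 | 45% v 15% | 4.64 | 77% |

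With equal recording (0.90 in both arms) the odds ratio is 1.0 and the error rate stays at the nominal 5%. Every value of p, a_E and a_C is an assumption.

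**The case against.** The strongest reply is that capture through conversation is an inference. The secondary data are to be collected at each visit in every arm, the final packet is the same for all, and Data Collection Sheet 1 may already ask each subject about each goal. That possibility stands. But nothing in the documents says that it does, or that the subject completes it apart from the pharmacist's discussion.

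A second reply is that the quoted item is a process log of who started a conversation and what it covered. This fits the use of patient-initiated discussion as an engagement covariate in Data Analysis. The text does not settle this. If it is a log, however, the plan describes no separate outcome record of goal progress, and the same change is needed.

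A third reply is weight: this is a feasibility-sized pilot, the outcome is secondary, aim 1 is worded descriptively, and the choice of dialysis modality is untouched. All of that is true and limits the importance of the point.

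Three stronger readings are tempting and are not supported:

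- *Goal selection in control is merely volunteered.* The table footnote asks every subject to set goals. The help given in Arm 1, "Pharmacist initiated review of workbook and assist with Action Plan goal selection", is part of the randomised intervention, so any effect on the goals chosen is a treatment effect.
- *All ten goals are affected.* Several have data collected without regard to arm.
- *Asking control about progress would itself break the design.* Recording a status is not reinforcement, so uniform asking is compatible with the control arm as described.

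**Conclusion.** The point holds for goal progress, and for goals without separate data. Followed as written, the plan ascertains progress through contacts that differ by arm and then compares arms on it. Recorded progress can therefore favour education with no true difference, and the comparison of staff time with outcomes carries the same fault.

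The size is unknown. A reader might take the table of odds ratios as an estimate of bias, but it only restates the assumed recording gap. The direction also rests on unrecorded progress being counted as none. The documents do not say how it would be coded, and if it were treated as missing, the direction would depend on which control subjects speak up.

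If Data Collection Sheet 1 already asks every arm the same progress questions, independently of the discussion, a sentence saying so resolves the point.

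**What to change.** Record goals chosen, and progress on each of the 10 performance goals, with one identical self-completed checklist in all arms, or as items on Data Collection Sheet 1 if it lacks them. Subjects complete it with the Visit 3 post-test, before any discussion with the pharmacist. State in Data Analysis that the between-arm comparison of goal progress, and its use in the cost comparison, rests on this instrument alone. Keep goal topics recorded in conversation as process data.

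The cost is one extra page in an existing packet and one sentence of analysis text. The checklist may prompt control subjects slightly, but it does so only at the post-test, when the visit-based outcomes are being collected, and in the same way in every arm. The content of the three arms is unchanged.
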